#### 4-weeks post-enrolment and 4-weeks prior to expected due date:

- Date of the visit.
- Serious adverse events (drug related or not) in the mother since previous visit/contact.
- Exacerbation of pre-existent clinical condition in the mother since previous visit/contact.
- Comorbidities in the mother since previous visit/contact.
- Concomitant medication use in the mother since previous visit/contact.
- Maternal complications since previous visit/contact.
- Fetal complications since previous visit/contact; any spontaneous abortions (≤28 weeks gestation), elective abortions, ectopic pregnancies, late fetal or neonatal deaths (>20 weeks gestation), premature deliveries (≤37 completed weeks).

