
## 5.4 Sample Size Calculation

Data for this pregnancy Registry will be regularly collected until the sample size required to detect a 2-fold or greater increase relative to the expected background rate of all birth defects and spontaneous abortions is reached. This will provide an adequate sample to ensure understanding of maternal drug safety. The Registry will be closed to new entries once this number of women with validated follow-up information has been reached and in agreement with the EMA; the data will be transferred to another independent Registry, if in acceptance with the other Registry, and according to ethical standards and national legislation at that point in time. These data will then be compared to background rates to see if there has been a significant increase in birth defects or pregnancy loss amongst these patients. A sensitivity analysis will be performed on the data to check other contributing factors.

The following sample size is derived to detect a clinically significant difference (i.e. a >2x increase in the outcome of concern) relative to expected background rates. In Europe, the assumed background risk of all reported birth defects is 23.719 per 1,000 births (EUROCAT, 2009) and the background rate of spontaneous abortion is 85.6 per 1,000 (Tata *et al*, 2005). Thus, assuming 80% power, 0.05 significance level (one-sided) and a loss to follow-up rate of 5%, we would require 376 pregnant women exposed to EurartesimTM in order to be able to detect a 2-fold or greater increase in birth defects and a 1.5-fold or greater incidence in spontaneous abortions with a one-group test. Calculations are based on a normal approximation to a Binomial distribution (equivalent to a chi-square test). Employing a 5% loss to follow-up rate is deemed appropriate as

utilising the services of ProClinica (refer to Section 7.3) to actively follow-up patients via direct patient contact should reduce the degree of loss to follow-up in this Registry.

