#### At end of pregnancy:

- Date of the end of pregnancy.
- Maternal complications since previous visit/contact.
- Maternal mortality.
- Stillbirth (>28 weeks gestation).
- Early neonatal mortality.
- Gestational age at delivery (estimated from the last menstrual period).
- Live births.

- Infant birth weight (adjusted for gestational age).
- Infant major and minor birth defects (primary outcome of interest).
- Serious adverse events (drug related or not) in the mother or the infant since previous visit/contact.
- Exacerbation of pre-existent clinical condition in the mother since previous visit/contact.
- Comorbidities in the mother since previous visit/contact.
- Concomitant medication use in the mother since previous visit/contact.

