#### Primary analysis

In accordance with the primary objectives of the study and the way the study was powered, the main focus of the statistical analysis will be estimation of the incidences of birth defects and spontaneous abortion. 95% confidence intervals will be computed around these incidences in order to judge whether there is an increase of these incidences as compared to background risks.

In order to control for potential confounders, birth defects and spontaneous abortion will be described according to parameters such as concomitant infections/diseases and medication use. For spontaneous abortions, women who discontinued the study prior to delivery will not be taken into account in the primary analysis. A sensitivity analysis will be performed considering all patients, assuming that women who discontinued the study prior to delivery had experienced spontaneous abortion; this will provide us with the highest estimation of incidence of spontaneous abortion (i.e. the worst-case scenario).

In the same way, in the primary analysis, incidences of birth defects will be analysed without considering patients who discontinued the study prior to 14 weeks after the end of pregnancy. A sensitivity analysis will be performed on all patients assuming that women who discontinued the study prior to 14 weeks after the end of pregnancy had experienced birth defects.

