#### Pregnancy-related information

Frequency and type of pregnancy outcome will be stratified by the earliest trimester of exposure, demographics and medical background characteristics. Gestational weeks will be counted from the date of the last menstrual period, with the second trimester as beginning at week 14 and the third trimester as beginning at week 28. Women who discontinued the study prior to delivery will not be taken into account in the primary analysis. A sensitivity analysis of patients who did not complete the entire follow-up will be performed for the main study outcomes, in the same manner as described above in the 'Primary analysis' section.

Time-to-event variables will be analysed via survival analysis methods (e.g. Kaplan-Meier survival estimates and associated confidence intervals).

In order to control for potential confounders, pregnancy outcomes will be analysed according to parameters such as lifestyle factors, concomitant infections/diseases and medication use. Patient's Body Mass Index (BMI) will be calculated from the patient's height (cm) and weight (kg) data, using the following equation:

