#### Secondary outcomes:

- Maternal complications.
- Maternal mortality (up to 6 weeks post-delivery).
- Spontaneous abortions (≤28 weeks gestation).
- Elective abortions.
- Ectopic pregnancies.
- Stillbirth (>28 weeks gestation).
- Premature deliveries ( $\leq$ 37 completed weeks).
- Early neonatal mortality ( $\leq 7$  days of birth).
- Neonatal mortality ( $\leq 28$  days of birth).
- Gestational age at delivery (estimated from the last menstrual period).
- Low birth weight (adjusted for gestational age).
- Infant development.

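### Premature delivery is defined as 37 or fewer completed weeks, so births in week 37 count as premature

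*Protocol*

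**What the plan says.** Section 7.4.1 names "Premature deliveries" among twelve secondary outcomes and limits it to 37 or fewer completed weeks. Section 5.5 lists the same outcome among the fetal complications to be recorded 4 weeks after enrolment and 4 weeks before the due date, as "premature deliveries (≤37 completed weeks". The data-collection part of the Summary repeats it. The three places agree, and none gives a source or a reason for the limit.

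Two related items bear on the point. The end-of-pregnancy list in Section 5.5 collects "Gestational age at delivery (estimated from the last menstrual period" as a separate item, and Section 7.4.1 lists it as an outcome in its own right. Section 5.7 fixes the counting rule: "Gestational weeks will be counted from the date of the last menstrual period".

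Prematurity has no part in the sizing or the main analysis. Section 5.7 states that "the main focus of the statistical analysis will be estimation of the incidences of birth defects and spontaneous abortion".

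**The concern.** The term completed weeks has a fixed meaning: a pregnancy of 37 weeks and 0 to 6 days has 37 completed weeks. A limit of 37 or fewer therefore takes in the whole of week 37, which is ordinarily counted as term. The usual preterm limit is fewer than 37 completed weeks, ending at 36w6d.

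This is a stated definition of a named safety outcome, not a detail left open for the analysis plan. Because the three statements agree, nothing in the text would prompt whoever builds the CRF or the tables to correct it.

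The registry has no control arm, so anyone who wants to interpret its prematurity rate is likely to set it beside an outside rate. An outside rate on the usual definition would not match, and the mismatch always points towards apparent harm.

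**Working it through.** **Plan's own figure.** There is none to reproduce. The protocol gives no expected preterm rate, no share of births in week 37 and no gestational-age distribution.

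**Step 1: which births the rule adds.** Count days from the last menstrual period, as Section 5.7 does for weeks.

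- 37w0d is day 37 × 7 = 259.
- Fewer than 37 completed weeks means up to day 258 (36w6d).
- 37 or fewer completed weeks means up to day 259 + 6 = 265 (37w6d).
- Difference: 265 − 258 = 7 days, the whole of week 37.

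**Step 2: effect on the rate.** Let p be the share of births before 37w0d and w the share from 37w0d to 37w6d.

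- Rate on the usual definition: p
- Rate on the protocol's definition: p + w
- Factor: (p + w) / p = 1 + w/p

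Both shares are assumptions. Over p = 5–20% and w = 4–10%:

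| p | w = 4% | w = 6% | w = 8% | w = 10% |
|---|---|---|---|---|
| 5% | 1.80 | 2.20 | 2.60 | 3.00 |
| 8% | 1.50 | 1.75 | 2.00 | 2.25 |
| 10% | 1.40 | 1.60 | 1.80 | 2.00 |
| 12% | 1.33 | 1.50 | 1.67 | 1.83 |
| 15% | 1.27 | 1.40 | 1.53 | 1.67 |
| 20% | 1.20 | 1.30 | 1.40 | 1.50 |

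The factor runs from 1 + 4/20 = 1.2 to 1 + 10/5 = 3.0. The upper end pairs the lowest assumed preterm share with the highest assumed week-37 share.

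**Step 3: effect in counts.** Section 5.4 plans 376 women with 5% loss to follow-up: 376 × 0.95 ≈ 357. If every one of these pregnancies reached a birth, 4–10% in week 37 would be 357 × 0.04 ≈ 14 to 357 × 0.10 ≈ 36 births labelled premature by the definition alone. The number is smaller to the extent that pregnancies end early.

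**Step 4: a narrower reading by sites.** If sites took the limit as 37w0d only, and week-37 births were spread evenly over seven days, the factor would be 1 + (w/7)/p. For p = 5–15% and w = 4–10% this runs from 1 + (4/7)/15 ≈ 1.04 to 1 + (10/7)/5 ≈ 1.29. That is not what completed weeks means, but it shows how much depends on how the rule is applied.

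**Step 5: whether week-37 births would be recorded.** The visit 4 weeks before the due date falls at about week 36, so it would miss most of them. Table 1 also schedules fetal complications at the end-of-pregnancy visit, and Section 5.5 places premature delivery under that heading. The outcome definition in Section 7.4.1 applies whichever visit captures the birth.

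**The case against.** The strongest defence is that little depends on this outcome. It is one of twelve secondary outcomes and carries no power calculation. The comparison of confidence intervals with background risk in Section 5.7 is for birth defects and spontaneous abortion only. Other pregnancy outcomes are stratified by trimester of exposure, demographics and medical background, and one cut-off applied to every stratum does not by itself create a difference between strata. No outside preterm rate is named as a comparator. Gestational age at delivery, the date the pregnancy ended and the due date or last menstrual period are all collected, so a rate on the usual definition can be tabulated later without new data. All of this stands, and it limits the harm.

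It is also true that the protocol does not contradict itself here. The charge rests on the ordinary meaning of preterm, which the protocol does not state, so a deliberate choice of the wider limit cannot be excluded. That is a reason to ask for a justification. It does not make the present text safe, because no reason is given and the outcome as named would still include term births.

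A reader might go further and infer that the rate is inflated by at least 1.5-fold, or that the distortion is as large as the 2-fold rise the plan treats as clinically significant and so amounts to a false drug signal. The documents support neither. They hold no gestational-age data from which to fix a factor, and several assumed pairs in the table fall below 1.5. The 2-fold threshold in Section 5.4 is set for the sizing outcomes and their stated background rates, not for prematurity.

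**Conclusion.** The point holds as a definitional error in a secondary safety outcome. As written, all births at 37w0d to 37w6d count as premature, and the reported rate would be too high against any rate that uses the usual limit of fewer than 37 completed weeks.

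The direction is certain given that usual definition; the size is not. A factor of about 1.2 to 3.0 rests wholly on assumed shares of 5–20% of births before 37 weeks and 4–10% in week 37, and its upper end needs an extreme pair.

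The primary outcome, the 376-woman sample size and the planned comparisons with background risk are untouched. The error can be undone from recorded gestational age, but the outcome the protocol names would still be reported wrongly unless the definition is changed.

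**What to change.** Define premature delivery as fewer than 37 completed weeks (up to 36w6d) in the Summary, Section 5.5 and Section 7.4.1, and state that it is derived from the recorded gestational age at delivery, not from a separate site judgement. If 37 or fewer completed weeks is intended, give the reason and compare the result only with rates that use the same limit.

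The cost is one changed symbol in three places and a sentence on derivation. No new data item, visit or change to the sample size is needed.

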#### At end of pregnancy:

- Date of the end of pregnancy.
- Maternal complications since previous visit/contact.
- Maternal mortality.
- Stillbirth (>28 weeks gestation).
- Early neonatal mortality.
- Gestational age at delivery (estimated from the last menstrual period).
- Live births.

- Infant birth weight (adjusted for gestational age).
- Infant major and minor birth defects (primary outcome of interest).
- Serious adverse events (drug related or not) in the mother or the infant since previous visit/contact.
- Exacerbation of pre-existent clinical condition in the mother since previous visit/contact.
- Comorbidities in the mother since previous visit/contact.
- Concomitant medication use in the mother since previous visit/contact.

#### 6 weeks after end of pregnancy:

- Date of the visit.
- Maternal complications since previous visit/contact.
- Maternal mortality.
- Early neonatal mortality ( $\leq 7$  days of birth).
- Neonatal mortality ( $\leq 28$  days of birth).
- Infant major and minor birth defects.
- Serious adverse events (drug related or not) in the mother or the infant since previous visit/contact.

#### 14 weeks after end of pregnancy:

- Date of the visit.
- Maternal complications since previous visit/contact.
- Maternal mortality.
- Infant mortality.
- Serious adverse events (drug related or not) in the mother or the infant since previous visit/contact.

- Infant development.

#### 12 months after end of pregnancy:

- Date of the visit.
- Serious adverse events (drug related or not) in the mother or the infant since previous visit/contact.

## 5.5.1 Infant development / assessment of pregnancy outcomes

# Enrolment visit / 4-weeks post-enrolment / 4 weeks prior to the expected due date:

Pregnant women exposed to Eurartesim™ for malaria will be primarily enrolled into this Registry via their Infectious Disease Doctor. During enrolment, the patient will be asked to consent to allow ongoing contact between ProClinica (refer to Section 7.3) and her obstetrician/gynaecologist (OB/GYN), General Practitioner (GP) and Paediatrician in order to co-ordinate active follow-up and completion of the CRF at the specified time-points. Throughout the patient's pregnancy, ProClinica will support the primary investigator by contacting the patient's OB/GYN and GP in order to obtain medical confirmation of events occurring, e.g. SAEs, comorbidities, maternal complications, fetal complications.

#### At birth:

At birth, ProClinica will contact the patient's OB/GYN and GP to obtain medical confirmation of events occurring, e.g. premature delivery, still birth, birth defects.

# 6 weeks after end of pregnancy / 14 weeks after end of pregnancy / 12 months after end of pregnancy:

After birth, ProClinica will contact the infant's Paediatrician to obtain medical confirmation of events occurring, e.g. birth defects, infant development, neonatal death.

"Birth defect" will be defined as a major congenital abnormality or syndrome with exclusion for related minor abnormalities, as defined by EUROCAT (EUROCAT, 2009). HCPs will record any infant birth defect(s) on the CRF via free text. This will then be coded in-house using both MedDRA and ICD-10 codes (ICD-10 Chapter XVII: congenital malformations, deformations and chromosomal abnormalities, as recommended by EUROCAT) to enable comparisons and transfer of data between other sources.

## 5.6 Monitoring visit

CRAs (Clinical Research Associates) will perform on-site monitoring visits for data quality checking in 20% of total sites dependent on an escalated monitoring procedure, which considers the compliance of each site with study procedures. The aim of these on-site visits will be to check the correct collection of informed consent, check key data of the CRF against the source data on a defined percentage of patients, check the correct reporting of adverse reactions according to the protocol and communicate with the HCP. These monitoring visits will also enable the CRA to resolve any administrative issues, potential logistical problems raised by the HCP and to discuss the recruitment of patients and compliance.

## 5.7 Statistical analysis

Statistical analyses will be carried out using SAS software version 9.2.

R-M EU will prepare a statistical analysis plan to be reviewed by Sigma-Tau and the CAB.

At regular intervals tables and listings will be produced to enable reporting of key interim outcomes to regulatory authorities, participating HCPs and the scientific/medical community at large.

Reporting of data (other than individual reports concerning individual patients or participating HCPs to those individual participants), will be in aggregate form to ensure individual patient and HCP confidentiality.

All analyses, primary and secondary, will be conducted in two manners:

- 1. On all women.
- 2. Stratifying the women depending on whether they were directly exposed to Eurartesim™ or whether the biological father was exposed to Eurartesim™.

#### Primary analysis

In accordance with the primary objectives of the study and the way the study was powered, the main focus of the statistical analysis will be estimation of the incidences of birth defects and spontaneous abortion. 95% confidence intervals will be computed around these incidences in order to judge whether there is an increase of these incidences as compared to background risks.

In order to control for potential confounders, birth defects and spontaneous abortion will be described according to parameters such as concomitant infections/diseases and medication use. For spontaneous abortions, women who discontinued the study prior to delivery will not be taken into account in the primary analysis. A sensitivity analysis will be performed considering all patients, assuming that women who discontinued the study prior to delivery had experienced spontaneous abortion; this will provide us with the highest estimation of incidence of spontaneous abortion (i.e. the worst-case scenario).

In the same way, in the primary analysis, incidences of birth defects will be analysed without considering patients who discontinued the study prior to 14 weeks after the end of pregnancy. A sensitivity analysis will be performed on all patients assuming that women who discontinued the study prior to 14 weeks after the end of pregnancy had experienced birth defects.

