In a further study, Rijken *et al* (2008) treated 50 pregnant women with recurrent Plasmodium falciparum infections (despite 7 day treatments with quinine or artesunate (+/- clindamycin) or both) with DHA-PQP. The gestational age at DHA-PQP treatment was 23.7±8.2 (9.2–39.1) weeks. 45 of the women had a known pregnancy outcome. Two infants were reported to be abnormal at birth; one with a small umbilical hernia (exposed to treatment at 24 weeks) and one diagnosed clinically with Patau syndrome (trisomy 13) (exposed to treatment at 34 weeks), who subsequently died at 6 hours of age. The remaining infants were all observed at 1 month of age and found to be healthy. The two abnormalities identified in the newborns are unlikely to be drug related. Thus, DHA-PQP was effective and well tolerated and there was no evidence of toxicity for the mothers or the newborns.

The phase four trial, or post-marketing phase, where the drugs are already in use on the markets, seeks to examine the risks and benefits of the new drug in different and larger segments of the population. This phase is important because it examines issues such as the longer-term effects of drug exposure on larger populations. Post-marketing surveillance is also important because even the most well designed phase three studies might not uncover every problem that could become apparent once a product is widely used. Furthermore, the new product might be more widely used by groups that might not have been well studied in the clinical trials and there might be reports of adverse drug reactions once a drug becomes available on the open market (African Media and Malaria Research Network, 2010).

This epidemiologic surveillance registry is necessary because of the potential for exposure in the first trimester of pregnancy and the unknown risks in pregnancy for any new chemical entity. The current lack of data regarding Eurartesim™ use during pregnancy makes such a registry an essential component of the ongoing assessment of

the safety of Eurartesim™. Through the registry, patients exposed to any formulation of Eurartesim™ during pregnancy will be registered by healthcare providers (HCPs), the pregnancies followed and the outcomes ascertained through follow-up. This information will be used to detect any potential risks to pregnant women and/or teratogenic effects in pregnancies exposed to any formulation of Eurartesim™.

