## 5.2 Selection criteria

#### Inclusion Criteria:

The following patients will be included in the study:

- Women;
  - who have received Eurartesim™ for malaria whilst pregnant, within one (1) month (30 days) before or at any time after conception, or
  - whose partner (the biological father) has received any formulation of Eurartesim™ for malaria within one (1) month (30 days) prior to conception (Committee for Medicinal Products for Human Use, 2005), and
  - who have been informed and agree to participate in this study.

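### The primary spontaneous-abortion proportion keeps women who were no longer at risk in its denominator, which dilutes the powered comparison with the background rate

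*Protocol*

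**What the plan says.** - **Eligibility (Protocol, 5.2).** A woman qualifies if she received the drug "within one (1) month (30 days) before or at any time after conception". There is no upper gestational limit. Exposure through the biological father in the 30 days before conception also qualifies.
- **Event (Protocol, 7.4.1).** The outcome is listed as "Spontaneous abortions (≤28 weeks gestation"). Stillbirth is a loss after 28 weeks.
- **Estimate (Protocol, 5.7, Primary analysis; repeated in the Summary).** The incidences of birth defects and spontaneous abortion are the main focus. Each gets a 95% confidence interval that is set against the background risk. Analyses are done on all women and then split by maternal or paternal exposure.
- **Denominator (same place).** "For spontaneous abortions, women who discontinued the study prior to delivery will not be taken into account in the primary analysis". A worst-case sensitivity analysis brings these women back and counts each as an abortion.
- **Benchmark and power (Protocol, 5.4).** "the background rate of spontaneous abortion is 85.6 per 1,000", and 376 women are to allow detection of a "1.5-fold or greater incidence in spontaneous abortions with a one-group test".
- **Related text.** Section 5.7 (Pregnancy-related information) stratifies the type of pregnancy outcome by earliest trimester of exposure, with the third trimester starting at week 28. It also mentions Kaplan-Meier methods for time-to-event variables that it does not name.

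**The concern.** A woman first treated at 30 weeks cannot have a spontaneous abortion as the protocol defines it, but she adds one to the denominator of the comparison. A woman who enrols at 18 weeks with a continuing pregnancy has already come through part of the risk period. Both pull the observed proportion below what a whole-pregnancy risk would give, while the benchmark stays at a single figure with no gestational window stated.

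Embryolethality is a hazard that the protocol's own introduction names. If enough late-exposed women enrol, an interval that includes 85.6 per 1,000 could not be read as reassurance.

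The discontinuation rule adds a smaller error. A woman lost to the study at 30 weeks is a known non-event. The primary analysis drops her, and the worst-case analysis counts her as an abortion.

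**Working it through.** **Inputs.** From 5.4: background p0 = 0.0856; 1.5-fold alternative p1 = 1.5 × 0.0856 = 0.1284; one-sided 5% level; 80% power; 5% loss; 376 women. Evaluable women: 376 × 0.95 = 357.

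**The plan's own figure.** 5.4 states "the assumed background risk of all reported birth defects is 23.719 per 1,000 births". An exact one-sided binomial test of 0.023719 against 0.047438 first reaches 80% power at n = 357 (reject at 14 or more events, level 0.048, power 0.801), and 357/0.95 = 376. So 376 is reproduced, through birth defects. The normal approximation that 5.4 names would give 328, or 345 after loss; this does not affect what follows. For spontaneous abortion at n = 357, the exact test rejects at 40 or more events (level 0.0495) and has power 0.842 against 0.1284.

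**Dilution.** Let f be the share of analysed women who cannot have the event because they were first exposed after 28 weeks, or enrolled after it with a continuing pregnancy. Give everyone else the full raised risk. Then

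expected proportion = 0.1284 × (1 − f), and power = P(X ≥ 40) with X ~ Binomial(357, 0.1284 × (1 − f)).

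| f (assumed) | Expected proportion | Ratio to 0.0856 | Exact one-sided power |
|---|---|---|---|
| 0 | 0.1284 | 1.50 | 0.84 |
| 10% | 0.1156 | 1.35 | 0.61 |
| 20% | 0.1027 | 1.20 | 0.31 |
| 30% | 0.0899 | 1.05 | 0.09 |
| 33.3% | 0.0856 | 1.00 | 0.05 |

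A 1.5-fold rise is fully hidden when 1 − f = 1/1.5, that is, when one third of the women are not at risk. 5.7 uses 95% intervals and two-sided tests. On that footing the normal-approximation powers for f = 0, 10%, 20% and 30% are 0.78, 0.52, 0.23 and 0.05.

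**What f might be.** The protocol gives no exposure timing for the registry. The only timing figure in it is from a cited series of 50 women (Section 3): "The gestational age at DHA-PQP treatment was" 23.7 ± 8.2 weeks, range 9.2 to 39.1. If the shape is roughly normal, z = (28 − 23.7)/8.2 = 0.524. The share after 28 weeks is then 0.30, or 0.29 if the normal is truncated to the observed range.

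**After restricting to women at risk.** The ratio returns to 1.5, apart from women who enter in mid-pregnancy, but fewer women count:

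- f = 20%: 357 × 0.8 = 286 women; reject at 33 or more; exact one-sided power 0.77.
- f = 30%: 357 × 0.7 = 250 women; reject at 30 or more; exact one-sided power 0.68.

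The corresponding powers as the plan is written are 0.31 and 0.09.

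**The case against.** **The trimester stratification.** It would show third-trimester women separately, at a boundary that almost coincides with the abortion cut-off, so a first-trimester excess could be seen. This stands as a partial safeguard, and it would be wrong to say that the plan ignores gestational timing. But the stratification is descriptive, it is not tied to the primary comparison, and no trimester-specific background is given.

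**The direction.** A reader might infer that the registry as a whole is biased toward safety. The documents do not support that. Section 5.5 lets women enrol with the pregnancy outcome already known, and 6.1 accepts that women with a known bad outcome may be more likely to enrol. That pushes the proportion up. Dropping late-lost non-events also pushes it up, although assumed loss is only 5%. What is established is that this one feature dilutes; the net direction is open.

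**The size.** A reader might take power of 9% as the registry's power. It is one scenario. The 30% share comes from a small series of recurrent infections and an assumed normal shape. The registry also takes women exposed before conception or only through the father, who carry the whole risk period. In the other direction, the table gives full risk to everyone exposed by 28 weeks, so entry in mid-pregnancy would add dilution.

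**The benchmark.** The title of the cited reference might suggest that 85.6 per 1,000 describes women with celiac disease. The protocol does not say which group in that study the rate comes from, so nothing can be concluded.

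**Left to the SAP.** Censoring and delayed entry are ordinary SAP content, and their absence is no fault here. The denominator rule is different, because the protocol itself fixes it.

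**Conclusion.** The point holds. Three rules that the protocol fixes do not fit together: exposure at any gestational age, an event limited to 28 weeks, and one primary proportion that excludes only women who discontinued before delivery. The comparison with 85.6 per 1,000 is therefore diluted by women not at risk.

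With 10% to 30% such women, a true 1.5-fold rise would appear as 1.35 to 1.05 times background, and exact one-sided power would be 0.61 to 0.09 instead of 0.84. These figures rest on an assumed share, full risk in all other women and 357 evaluable women. Even at 10% the power is well below the planned 80%.

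Spontaneous abortion is listed as secondary in 7.4.1, but 5.7 gives it joint main focus and 5.4 powers the registry for it, so the denominator matters.

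There is also a smaller inconsistency. The data-collection list for the two antenatal follow-up contacts (5.5) has a category "late fetal or neonatal deaths (>20 weeks gestation"), which overlaps the abortion window. The outcome list in 7.4.1 divides cleanly at 28 weeks.

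**What to change.** 1. In 5.7 (Primary analysis) and the matching Summary text, restrict the primary spontaneous-abortion denominator to women exposed and enrolled while still at risk, that is, at 28 weeks or earlier.
2. Keep women known to be pregnant beyond 28 weeks as non-events. Do not drop them from the primary analysis or count them as abortions in the worst-case analysis.
3. Add, as a supporting analysis, a cumulative incidence by gestational age with delayed entry. This handles women who enter in mid-pregnancy. Abortions already known at enrolment would fall outside its risk set, so report them separately.
4. In 5.4, restate the power for spontaneous abortion for the expected number of at-risk women, over a stated range of shares.
5. Reconcile the category for losses after 20 weeks in 5.5 with the 28-week definitions in 7.4.1.

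**Cost.** The dates needed (last menstrual period, exposure, visit, end of pregnancy) are already collected. The real price is precision: exact one-sided power of about 0.77 with 286 at-risk women and 0.68 with 250. By the normal approximation, 80% power needs 301 at-risk women. That means enrolling 301/(0.8 × 0.95), about 397, or 301/(0.7 × 0.95), about 453, against 376. Since 6.1 names recruitment as the main limitation, the sponsor may have to accept the lower power and say so.
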